Manual of Procedures (MOP) – The MOP will describe the sequence of study conduct and provide detailed instruction for the performance of screening, baseline, enrollment, treatment allocation and follow-up procedures. The MOP will provide instruction in case report form completion, use of the electronic data management system, and collection, documentation and transfer of specimens and tests to laboratories and reading centers.

Training and certification procedures – The CT Reading Center, in conjunction with the DCC, will conduct a training session before the study starts to train and certify personnel in the performance of study procedures.

CT technologists should have appropriate knowledge of cross-sectional anatomy, physiology, and pathology related to the heart. Technologists must be certified as RTs in their state. It is recommended that technologists also have at least two years of experience in chest computed tomography. The technologist should also have a basic knowledge of cardiac CT, knowledge of computer software applications, data formatting, and experience with the workstations and data formatting / transmission procedures used.

Each technologist involved in the study should also have a complete understanding of this protocol, be experienced at providing breath-holding instruction, ECG gating, and operation of the CT. To ensure quality control, each site should have designated CT technicians who will perform the examinations.

Training will be performed using a standard training PowerPoint presentation and interactive internet and teleconference system to train technologists. This allows ongoing training and certification of technologists. Other NIH studies have demonstrated that there will be a turnover of technologists, and doing on-site training for each technologist is not possible or practical. Using the standard interactive presentation and teleconference, each site can get specific training and follow-up as needed. Further, quality assurance will be performed on each scan (see below), and necessary feedback given to the specific technologist promptly (within 1-2 days) after the scan is received at the reading center. This will allow for rapid identification of improper scan techniques and has been shown to dramatically decrease inadequate data sets in previous multicenter studies done at this core reading center.

Site visits – Findings from site visits will be used to resolve problems and develop corrective action plans.

External data sources – The DCC will monitor quality control of data received from the CV reading center.

Internal quality control procedures – A data validation plan, rule set specifications, and programming logic to implement data validation rules will be implemented.

Routine reports

The DCC will develop a set of standard enrollment, tracking, quality review, and safety monitoring reports. Adverse event reports, DSMB reports and reports for statistical analysis will be developed and produced on an appropriate schedule.

Urgent Alerts

Several safety alerts (e.g. aortic aneurysm [$> 5\text{cm}$], severe coronary artery disease [defined as left main or 3 vessel disease], non-calcified lung masses [$>6\text{mm}$] and large pericardial effusions) will require urgent notification and reports forwarded to the local participating clinical centers by the Reading Center PI. The Reading Center PI will be responsible for notification of both the trial site PI and study coordinator, as well as the Data Coordinating Center within 24 hours. The site PI will then be responsible for notifying the subject within the following 24 hours and also notifying the Data Coordinating Center that the subject has been contacted.

Data Security

The data management system will be the same as the main Testosterone Trial Study designed to prevent unauthorized access to trial data and to prevent data loss due to equipment failure or catastrophic events. The procedures to do so encompass user account management, user privilege assignment, data loss prevention (database backup), computer systems validation, performance monitoring, and DMS change management. User access will be controlled by assignment of confidential usernames, passwords and role assignment. The system will meet the applicable Federal regulatory requirements and those described in the E6 Good Clinical Practice Guidelines to ensure the confidentiality of trial subjects.

Maintaining Anonymity of Submitted Medical Records

Clinical site personnel will de-identify all medical records before sending them to the DCC by obliterating any Protected Health Information (PHI). Upon receipt, DCC personnel will review the records to ensure that no PHI is visible.

Confidentiality

Information about study subjects will be kept confidential and managed according to the requirements of the Health Insurance Portability and Accountability Act (HIPAA) of 1996.

References

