The study will be conducted at nine trial sites across the United States. The CT reading center at Los Angeles Biomedical Research Institute at Harbor-UCLA will coordinate the CT angiography studies. The Clinical Research Computing Unit at the University of Pennsylvania will be the Data Coordinating Center, and other central services will be the same as for The Testosterone Trial.

Study Endpoints

Cardiovascular Trial Endpoints

Primary Endpoint: Change in atherosclerotic plaque burden from 0 to 12 months, as assessed by cardiac CT angiography

Exploratory Endpoints:

- Coronary artery calcium by CT scan
- Visceral and subcutaneous fat by CT
- Lipids, lipoproteins, and lipid particle size
- Markers of glucose metabolism: fasting glucose and insulin, hemoglobin A1c
- Markers of inflammation, coagulation, endothelial dysfunction, and myocardial damage

Early Withdrawal of Subjects

Because these trials are based on the principle of “intent-to-treat”, every attempt will be made to follow and evaluate all enrolled subjects for the duration of the trials. Therefore, even if treatment is discontinued, the subject will be asked to complete the appropriate evaluations. If subjects develop renal insufficiency or develop a significant contrast allergy prior to follow up CT scan, a follow up contrast scan will not be conducted. These subjects will not be withdrawn from the CV trial, but will undergo a non-contrast calcium scan at 12 months, rather than a contrast study.

Subject Selection and Withdrawal

Number of Subjects

Subjects will be evaluated for study eligibility during their screening process for the main T Trial. Please note that if each of the main trials (Vitality, Physical Function, and Sexual Function) within the Testosterone Trial has met its

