enrollment goals, subjects will be required to be eligible for and to participate in either the Bone Trial or the CV Trial, if they are still open to enrollment. At that time, all subjects who are screened for the Testosterone Trial will also be screened for the Cardiovascular Trial. In addition, all subjects who sign the T Trial baseline consent form will also receive details about the Cardiovascular Trial and will consent to the Cardiovascular trial. . The number of subjects will be 160 for CT angiography studies. Each of the nine sites is expected to enroll approximately 20 participants until the goal of 160 is reached. However, sites who are enrolling at a higher rate should continue to enroll in the trial above 20 participants, until the overall recruitment goal is met. It is projected that 85% of subjects allocated to treatment will complete the 12 months of treatment and be available for follow up measures by CT.

Inclusion Criteria for the Cardiovascular Trial

- Normal baseline renal function as assessed by eGFR (estimated glomerular filtration rate) > 60 ml/min/1.73m² at Screening Visit 1 and Month 12
- Willingness to consent and participate

Exclusion Criteria for The Cardiovascular Trial

- Weight >300 pounds
- Known allergy to iodinated contrast medium
- Inability to breath-hold for 10 seconds
- Current diagnosis of active atrial fibrillation
- Prior coronary artery bypass grafting by patient report or medical records

Trial Sites

The Cardiovascular Trial will be conducted at 9 of the 12 sites in The Testosterone Trial. These sites all have 64-slice MDCT scanners and sufficient experience using them, as determined by a questionnaire completed by the sites. Subjects will be identified and recruited by coordinators at the 9 sites with sufficient cardiac CT capabilities as identified by prior survey. The coordinators will approach patients for interest in participation in The Cardiovascular Trial.

CT Scanning

CT Reading Center

The Reading Center for CTA will be based at the Los Angeles Biomedical Research Institute at Harbor-UCLA and directed by [name]. The Center will coordinate and oversee the collection of the data, store backup copies of the data, read each scan, send the results to the DCC and maintain quality control.

Subject participation

The Testosterone Trial site staff will communicate with the eligible subjects to explain the cardiac CT measurements and provide information concerning

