For eventual determination of microparticles, 10 mL of citrated blood will be centrifuged at 1,500 g for 15 minutes. The supernatant will then be centrifuged at 13,500 g for 5 minutes to remove the platelets. The resulting supernatant of platelet-free plasma will be frozen, shipped to the central laboratory on dry ice, and stored at -80° C until assay. Samples will be frozen and thawed only once.

Cardiovascular Events Ascertainment and Adjudication

See the T Trial Cardiovascular Event Adjudication Manual for a complete description of the ascertainment and adjudication process.

Study Procedures and Visits

Prescreening/Screening Visit 1/Screening Visit 2 Men will be screened over the phone and in person to determine if they qualify for the CV study. Screening for the CV Trial will take place over the course of the telephone screen, Screening Visit 1 and Screening Visit 2 of the Main T Trial.

Baseline Visit

- Sign Baseline consent form
- CT scan without and with contrast for coronary artery calcium score, non-calcified plaque volume, and total plaque volume
- CT scan for visceral and subcutaneous on three slices through abdomen at L3-4

Month 12 Visit

- Re-evaluation of medical history for development of allergy to iodinated contrast medium
- Review of renal function based on month 12 e-GFR calculation (> 60 ml/min/1.73m²)
- CT scan including coronary artery calcium score, non-calcified plaque volume, total plaque volume
- CT scan for visceral and subcutaneous on three slices through abdomen at L3-4

Subject Compensation

Subjects will be compensated during the course of the trial, \$50 for the baseline visit and for the month 12 visit, for a total of \$100 if a subject completes the trial. In addition, subjects will be compensated for travel and parking and provided meal tickets for study visits.

Statistical Plan

Analytical Methods and Sample Size Estimations

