Although this Trial will not likely have adequate power to detect a difference between treatment groups in incidence of clinical cardiac events, we shall track and adjudicate cardiovascular events in all subjects in all trials to look for trends. Additionally, although this trial is designed to test whether treatment with testosterone reduces volume of coronary plaque compared with placebo treatment, the supporting data are limited and we recognize that effects in either direction could be observed. Given the increasing use of testosterone in elderly men, data suggesting that testosterone treatment decreases or increases plaque volume would be valuable. As for all other hypothesis tests in The Testosterone Trial, two-sided tests will be performed and will permit conclusions regarding effects in either direction.

Safety and Adverse Events

Definitions

Definitions are per the January 2007 Guidance on Reviewing and Reporting Unanticipated Problems Involving Risks to Subjects or Others and Adverse Events, Office on Human Research Protection (OHRP) Guidance. <http://www.hhs.gov/ohrp/policy/AdvEvtGuid.htm>. The requirements and processes for reporting adverse events are described in the corresponding National Institute on Aging (NIA) Guidelines and collected as per the main Testosterone Trial protocols.

Abnormal Laboratory Values

A clinical laboratory abnormality should be documented as an adverse event if any one of the following conditions is met:

- The laboratory abnormality is not otherwise refuted by a repeat test to confirm the abnormality.
- The abnormality suggests a disease and/or organ toxicity.
- The abnormality is of a degree that requires active management.

- Creatinine will be specifically assessed to evaluate safety of contrast administration

Safety Measures Related to CT Angiography.

Use of CT angiography raises two important safety issues: the amount of radiation absorbed by the body tissues and the exposure to iodinated contrast agents, which have the potential to produce allergic reactions and acute renal injury. A number of strategies have now been validated to lower the radiation dose of CT angiography to just above background doses.

Allergy to Contrast Media.

Subjects will be asked at the baseline and 12 month Testosterone Trial visit if they have a known allergy to contrast media. Subjects with known or suspected contrast allergy will not be eligible for the CV trial.

Renal Function.

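### The exclusion list bars only a known contrast allergy, the safety section bars known or suspected, and the screening question asks only about known

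*Protocol*

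**What the plan says.** Four parts of the protocol deal with contrast allergy.

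- **Exclusion Criteria for The Cardiovascular Trial** lists "Known allergy to iodinated contrast medium". Suspected allergy is not mentioned.
- **Allergy to Contrast Media** (safety section) first sets the question: "Subjects will be asked at the baseline and 12 month Testosterone Trial visit if they have a known allergy to contrast media". It then states the bar: "Subjects with known or suspected contrast allergy will not be eligible for the CV trial".
- **Early Withdrawal of Subjects** covers men already enrolled. If they "develop a significant contrast allergy prior to follow up CT scan, a follow up contrast scan will not be conducted". Their status is also settled: "These subjects will not be withdrawn from the CV trial, but will undergo a non-contrast calcium scan at 12 months".
- **Month 12 Visit** lists "Re-evaluation of medical history for development of allergy to iodinated contrast medium", with no qualifier on the kind of allergy.

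The Baseline Visit list shows what follows for a man who is admitted: "CT scan without and with contrast for coronary artery calcium score". The protocol does not define known, suspected or significant, and does not say which section governs where they differ.

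**The concern.** A site normally checks eligibility against the inclusion and exclusion lists. Here the list is narrower than the safety section, and the only question the protocol prescribes is as narrow as the list. A coordinator who follows both to the letter can enrol a man whom another page of the same protocol excludes, and that man is then scheduled for iodinated contrast.

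The protocol itself treats this exposure as one of two important safety issues with CT angiography. With nine sites enrolling, the decision could also differ between sites according to the section each works from.

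**Working it through.** The plan gives no figure to reproduce and no arithmetic applies. The check is to take each kind of man through the rules as written.

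**Entry**

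| Man at baseline | Exclusion list | Prescribed question | Safety-section bar | Consistent? |
|---|---|---|---|---|
| Known allergy | Excluded | Detected | Ineligible | Yes |
| Suspected, not known | Not excluded | Not asked about | Ineligible | No |
| Neither | Not excluded | Nothing to detect | Not barred | Yes |

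The conflict is confined to the middle row, where two separate defects meet:

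1. The list and the safety section disagree on whether suspected allergy excludes a man.
2. Within the safety section, the question is narrower than the bar in the next sentence. A man with only a suspected allergy can truthfully answer no.

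Together they leave no step in the protocol text that stops him before the baseline contrast scan, although one sentence says he should not be in the trial.

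**Month 12**

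| Section | What triggers it | Stated consequence |
|---|---|---|
| Early Withdrawal of Subjects | New significant allergy | No contrast; stays in the trial with a non-contrast calcium scan |
| Month 12 Visit | Any development of allergy | Re-evaluate history; no consequence given |
| Allergy to Contrast Media | Question on known allergy, followed by a bar on known or suspected | Not eligible for the trial |

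For a new significant allergy, Early Withdrawal of Subjects gives a clear answer on both contrast and retention. Two things stay open. The first is what happens after a suspected or lesser reaction, on which that section is silent. The second is whether the ineligibility sentence is meant to apply again at month 12, since the question it follows is put at both visits. The protocol does not reserve eligibility language strictly for entry: the inclusion list sets its eGFR criterion at Screening Visit 1 and also at Month 12. The second reading is therefore possible, but it is not required.

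**The case against.** The strongest reply is that both entry rules can be obeyed at once. An exclusion list says who is out; it does not order the admission of everyone it omits. A site that reads the whole protocol would exclude known allergy under either section and suspected allergy under the safety section. On this view the list is merely incomplete. Screening also runs over a telephone call and two visits, and detailed instructions are left to a Manual of Procedures that is not shown and may ask more.

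This limits the point but does not remove it. The protocol is the controlling document, its two statements of who is ineligible differ, and the one question it prescribes matches the narrower of them. A manual may help in practice but would not reconcile the protocol text.

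The reply does succeed against three stronger readings that a reader might infer:

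- *That the same man is both given and refused contrast.* No section orders contrast for a suspected or mild reaction. That he could receive it follows only from the list and the question failing to stop him.
- *That three thresholds govern one decision.* The word significant applies to allergy that develops after entry, and it decides only whether the second scan uses contrast. It does not contradict the entry list. It meets the safety section only if the ineligibility sentence applies again at month 12.
- *That month 12 follow-up would be lost.* Early Withdrawal of Subjects already keeps these men in the trial. A site would have to disregard the rule written for exactly this situation.

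**Conclusion.** The entry inconsistency stands on the text alone, without an assumed rate or a contested reading. It concerns men with a suspected but not known contrast allergy. The month 12 point is a secondary ambiguity, and the conflict with the ineligibility sentence depends on that sentence being read as applying again at that visit.

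The number of men affected cannot be given. A reader might apply an assumed 1% to 5% to the 160 men and obtain 160 × 0.01 = 1.6 to 160 × 0.05 = 8. The documents do not support that range. They state no rate, a rate for any possible reaction would include known allergies that both sections bar, and 160 is the enrolment target, not the number screened.

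No stated sample-size figure is affected. Nothing in the documents suggests that the inconsistency would act differently in the two arms of this double-blind trial. The matter is one of eligibility and contrast exposure. It is worth correcting because the remedy is small and the protocol itself names the exposure as a safety issue.

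**What to change.** 1. Reconcile Exclusion Criteria for The Cardiovascular Trial and Allergy to Contrast Media to one entry definition. The sponsor chooses it; this review takes no position on which is right.
2. Word the screening question so that it asks about everything the chosen definition bars.
3. Tie the ineligibility sentence in Allergy to Contrast Media expressly to entry.
4. Align the month 12 wording in Early Withdrawal of Subjects, Month 12 Visit and Allergy to Contrast Media, so that the check decides only whether contrast is given. Follow-up stays as Early Withdrawal of Subjects already states. The sponsor sets the criterion for withholding contrast.

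The cost is a short amendment, including the wording of the screening question. If the wider entry definition is chosen, a few more men would be screened out.
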